8.5 Additional Analysis

This section describes analysis of TSQM domains. Analyses of other exploratory assessments mentioned in the protocol may be described in a separate document. The description of analyses of additional variables of SwCl is also included.

8.5.1 Analysis of TSQM Domains

TSQM is a widely used generic measure of satisfaction with medication and has been demonstrated to be a valid and reliable measure of satisfaction in patients with CF¹⁰. It consists of 14 items to form 4 domains: effectiveness (items 1, 2, 3), side effects (items 4, 5, 6, 7, 8), convenience (items 9, 10, 11), and global satisfaction (items 12, 13, 14). The score of each domain is a scaled score that ranges from 0 (least satisfied) to 100 (most satisfied). Scaled score for each domain can be calculated using the scale scoring algorithm¹¹.

Absolute change from baseline in TSQM domains at Week 52 (only for subjects aged ≥12 years to <18 years at the date of informed consent) will be analyzed descriptively.

8.5.2 Analysis of Additional Variables for SwCl

Proportion of subjects with SwCl <60 mmol/L through Week 52 (pooled with data from Study 103): Analysis of this endpoint will be based on a GEE model similar to that for the proportion of subjects with SwCl <60 through Week 24 using the PFAS (8.3.2.2), with the addition of data from Week 36 and Week 52.

Proportion of subjects with SwCl <30 mmol/L through Week 52 (pooled with data from Study 103): Analysis of this endpoint will be based on a GEE model similar to that for the proportion of subjects with SwCl <30 through Week 24 using the PFAS (8.3.2.2), with the addition of data from Week 36 and Week 52.

9 SUMMARY OF INTERIM AND DMC ANALYSIS

9.1 Interim Analysis

No interim analysis is planned for this study.

9.2 DMC Analysis

The DMC will conduct planned safety reviews of study data as outlined in the DMC Charter. For the open session of each DMC meeting, selected tables will be presented for the overall treatment group based on blinded data. For the closed session, the analysis presentation will be by treatment group based on unblinded data (generated by the independent biostatistician).

11 LIST OF APPENDICES

Appendix A: Analysis Visit Windows for Safety and Efficacy Assessments

Table 11-1 Analysis Visit Windows for Safety and Efficacy Assessments

Assessment	Visit ¹	Target Study Day	Analysis Visit Window ^{2,3,4} (in study days)
Safety Assessments			

 • Pulse oximetry • Serum chemistry • Hematology (except HbA1c) • Vital signs (excluding BMI, height, weight) 	Day 1 (Baseline)	1	≤1 Pre-dose
	Day 15	15	[1, 22]
	Week 4	29	(22, 43]
	Week 8	57	(43, 71]
	Week 12	85	(71, 99]
	Week 16	113	(99, 141]
	Week 24	169	(141, 211]
	Week 36	253	(211, 309]
	Week 52	365	(309, 379]
	Safety Follow-up	Not applicable	Use nominal visit
HbA1c (%)	Day 1 (Baseline)	1	≤1 Pre-dose
	Week 12	85	[1, 127]
	Week 24	169	(127, 267]
	Week 52	365	(267, 379]
Standard 12-lead ECG	Day 1 (Baseline)	1	≤1 Pre-dose
	Day 15	15	[1, 22]
	Week 4	29	(22, 43]
	Week 8	57	(43, 85]
	Week 16	113	(85, 141]
	Week 24	169	(141, 211]
	Week 36	253	(211, 309]
	Week 52	365	(309, 379]
		Safety Follow-up	Not applicable
Coagulation	Day 1 (Baseline)	1	≤1 Pre-dose
	Week 12	85	[1, 127]
	Week 24	169	(127, 211]
	Week 36	253	(211, 309]
	Week 52	365	(309, 379]
		Safety Follow-up	Not applicable
Efficacy Assessments⁵			

 • Spirometry (in-clinic) • Height, weight, BMI, and z-scores 	Baseline	-	≤1 Pre-dose
	Day 15	15	[1, 22]
	Week 4	29	(22, 43]
	Week 8	57	(43, 85]
	Week 16	113	(85, 141]
	Week 24	169	(141, 211]
	Week 36	253	(211, 309]
	Week 52	365	(309, 379]
		Safety Follow-up	Not applicable

Table 11-1 Analysis Visit Windows for Safety and Efficacy Assessments

Assessment	Visit ¹	Target Study Day	Analysis Visit Window ^{2,3,4} (in study days)
Sweat Chloride	Baseline	-	≤1 Pre-dose
	Day 15	15	[1, 22]
	Week 4	29	(22, 71]
	Week 16	113	(71, 141]
	Week 24	169	(141, 211]
	Week 36	253	(211, 309]
	Week 52	365	(309, 379]
CFQ-R	Baseline	-	≤1 Pre-dose
	Week 8	57	[1, 85]
	Week 16	113	(85, 141]
	Week 24	169	(141, 267]
	Week 52	365	(267, 379]
TSQM	Baseline	-	≤1 Pre-dose
	Week 52	365	[1, 379]

Notes:

¹ Visit name for analysis purposes is used to report data in tables and figures.

² The analysis visit windows will be applied using the following rules for both scheduled and unscheduled visits:

- a. If no numerical measurement is available within a visit window, the measurement will be considered missing for the visit.
- b. If there is more than 1 numerical measurement available within a visit window, use the following rules:
 - i. The measurement closest to the target day will be used; or
 - ii. If there are multiple measurements with the same distance from the target day, the latest measurement will be used. If the latest measurement cannot be determined, and there are both scheduled and unscheduled visits, then the unscheduled visit will be selected.

³ For measurements collected on the date of first dose of study drug in the Treatment Period, if it cannot be determined whether a measurement is before or after the first dose:

- a. Scheduled measurements will be treated as pre-dose observations.
- b. Unscheduled measurements will be treated as post-dose observations.

⁴ For safety assessments, the Safety Follow-up analysis visit will be based on the nominal Safety Follow-up visit. If a subject does not have a nominal Safety Follow-up visit but has an early termination of treatment (ETT) visit with study day >379, then the ETT visit will be mapped to the Safety Follow-up analysis visit.

⁵ For efficacy assessments, if a subject has a nominal Safety Follow-up visit with study day >379, then the nominal Safety Follow-up visit will be mapped to the Safety Follow-up analysis visit; else if a subject does not have a nominal Safety Follow-up visit with study day >379 but has an ETT visit with study day >379, then the ETT visit will be mapped to the Safety Follow-up analysis visit; else if there are multiple assessments with study day >379, then the earliest record will be selected as the Safety Follow-up analysis visit.

Derived Variables:

1. Age (in years) at first dose date and at nominal visits (for demographics, listings, and the calculation of [percent] predicted spirometry variables):

Obtain the age at informed consent (in days) in “yy, mm” format (e.g., 24 years, 6 months) from the Vital Signs (VS) page at the Screening Visit, and add 15.22 days to convert to days.

Obtain the informed consent date.

Table 11-1 Analysis Visit Windows for Safety and Efficacy Assessments

Assessment	Visit ¹	Target Study Day	Analysis Visit Window ^{2,3,4} (in study days)

Then, age (in years) at first dose or nominal visit = [(first dose date or nominal visit date – informed consent date) in days + age at informed consent (in days)]/365.25.
 
2. Age (in months) at nominal visit (for calculation of BMI and z-scores, as applicable):
 
Obtain the age at informed consent (in months) in “yy, mm” format (e.g., 24 years, 6 months) from the VS page at the Screening Visit.
 
Obtain the informed consent date.
 
Then, age (in months) at nominal visit = integer part of {[age at informed consent (in months) + 0.5 + diff (nominal, informed consent date) in months]} + 0.5.
 
3. Missing first dose date or last dose date:
 
If the first dose date is missing, use the Day 1 visit date to impute.
 
If the last dose date is missing or a partial date is reported, the last dose date will be imputed based on, in descending order of priority, the ETT visit date, the last visit date before the Safety Follow-up visit, or the last study drug administration date from the EC SDTM domain, as appropriate. The imputation algorithm will ensure the imputed last dose date does not exceed the study participation end date.
 
4. Sweat Chloride:
 
Non-missing sweat chloride concentrations from the left arm and right arm with assessment end date/time for a given arm up to 30 minutes after the first dose time in the Treatment Period will be considered for baseline.
 
5. Electrocardiogram:
 
Baseline is defined as the most recent pre-treatment measurement before the first dose of study drug in the Treatment Period. If multiple ECG measurements are obtained on the same calendar day during the TE Period for the Treatment Period,
 
 ○ For summary purposes, the calculated average ECG will be used as the ECG value on that day; ○ For threshold analysis purposes, all reported ECG values will be used. 			

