### **9.1.5 Early Termination of Treatment**

If a subject prematurely discontinues study drug treatment, an Early Termination of Treatment (ETT) Visit should be scheduled as soon as possible after the decision to discontinue treatment. Subjects who prematurely discontinue treatment will also be required to complete the Safety Follow-up Visit, approximately 28 ( $\pm$  7) days after their last dose of study drug.

If the ETT Visit occurs 3 weeks or later following the last dose of study drug, then the ETT Visit will replace the Safety Follow-up Visit, and a separate Safety Follow-up Visit will not be required.

If a subject withdraws consent for the study, no further assessments will be performed. Vertex may retain and continue using the study data and samples after the study ends, and may use the samples and information in the development of the study compound, for other drugs and diagnostics, in publications and presentations, and for education purposes. If a subject withdraws from the study, the study data and samples collected will remain part of the study (Section 9.9).

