8 STATISTICAL ANALYSIS

8.1 General Considerations

The Schedule of Assessments is provided in the CSP for Study 102. The precision standards for reporting safety and efficacy variables are provided in an internal Biometrics document that specifies the programming rules including the precision for derived variables.

Continuous variables will be summarized using the following descriptive summary statistics: the number of subjects (n), mean, SD, median, minimum value (min), and maximum value (max).

Categorical variables will be summarized using counts and percentages. Percentages will be presented to 1 decimal place.

Baseline value:

For all safety endpoints:

- Unless otherwise specified, baseline will be defined as the most recent non-missing measurement (scheduled or unscheduled) collected before the first dose of study drug in the Treatment Period (i.e., the Day 1 Visit).

For all efficacy endpoints:

- Except for SwCl, baseline will be defined as the pre-dose Day 1 value. If the pre-dose Day 1 value is missing, the most recent pre-dose, non-missing value on or after the Day -14 visit, including unscheduled visits, will be used as baseline.
- For SwCl, baseline will be defined as the average of the two most recent pre-dose, non-missing values on or after the Day -14 visit, including unscheduled visits. If only 1 non-missing value is available during this interval, the available value will be considered as baseline.

Absolute change from baseline will be calculated as post-baseline value - baseline value.

Relative change from baseline will be calculated as (post-baseline value - baseline value)/baseline value.

The **Treatment-emergent (TE) Period for the Run-in Period** will be from the first dose date of study drug in the Run-in Period to (1) the first dose date of study drug in the Treatment Period for subjects who complete the Run-in Period and continue to the Treatment Period, or (2) 28 days after the last dose date of study drug in the Run-in Period or to the completion of study participation date, whichever occurs first, for subjects who do not continue to the Treatment Period (e.g., subjects who do not meet the conditions to enter the Treatment Period).

The **TE Period for the Treatment Period** will be from the first dose date of study drug in the Treatment Period (VNZ/TEZ/D-IVA or ELX/TEZ/IVA) to 28 days after the last dose date of study drug in the Treatment Period or to the completion of study participation date, whichever occurs first.

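### A partial last dose date can be replaced by an ETT or last-visit date outside the reported month or year, because the only stated cap is the end of study participation

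*SAP*

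**What the plan says.** SAP Appendix A, Derived Variables item 3, is triggered "If the last dose date is missing or a partial date is reported", so an incomplete date and an absent one are handled alike. The date is then "imputed based on, in descending order of priority, the ETT visit date, the last visit date before the Safety Follow-up visit", and third "or the last study drug administration date from the EC SDTM domain, as appropriate". One limit is stated: "The imputation algorithm will ensure the imputed last dose date does not exceed the study participation end date". Nothing ties the result to a month or year that the site did report.

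Protocol 9.1.5 times the ETT visit from the decision to stop: it "should be scheduled as soon as possible after the decision to discontinue treatment". The same section provides for a long gap: "If the ETT Visit occurs 3 weeks or later following the last dose of study drug", the ETT replaces the Safety Follow-up Visit.

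The last dose date sets the length of exposure (SAP 8.2.5), the compliance denominator (SAP 8.2.6) and the end of the TE Period, which runs "to 28 days after the last dose date of study drug in the Treatment Period" or to completion of participation if that is earlier (SAP 8.1). TEAE status (SAP 8.4.1) and the concomitant or post-treatment class of a medication (SAP 8.2.4) follow from the TE Period.

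**The concern.** A partial date carries information. If the site reports a month and year, the last dose cannot lie after the last day of that month. The rule can discard that and return a date that the reported data exclude.

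The SAP does not do this elsewhere. In Appendix B, a medication stop date lacking only the day becomes the last day of its month, and one lacking day and month becomes the last day of its year. In Appendix E, an AE end date lacking the day becomes the earlier of month end and end of participation. Of these stop and end dates, only the study drug's is not held to its known period.

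At stake is the timing of drug relative to events in subjects who stop early. Off-drug days may count as exposure, the compliance denominator may be too large, and some late events may be labelled treatment-emergent.

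**Working it through.** The plan states no figure on this point, so there is none to reproduce. The check is date arithmetic.

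**Contradiction with reported data (illustrative dates).** Last dose reported as March 2023, ETT on 20 April 2023. The rule's first source gives 20 April. The latest date consistent with the report is 31 March. The imputed date is therefore at least 20 days too late.

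**Notation.** L = true last dose, g = ETT date minus L in days, P = end of participation.

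**Exposure.** SAP 8.2.5 takes last dose minus first dose plus 1, so using the ETT date adds g days.
- g = 0 (ETT on the day of the last dose): no error.
- g = 21, true exposure 84 days: 21/84 = 25.0% too long.
- g = 21, true exposure 168 days: 21/168 = 12.5% too long.

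**TE Period.** Correct end: min(L + 28, P). End under the rule: min(L + g + 28, P). The difference is the number of extra TE days. Days below count from the true last dose.

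| Participation ends | g | Correct TE end | TE end under the rule | Extra days |
|---|---|---|---|---|
| Well after day 28 + g | 7 | 28 | 35 | 7 |
| Well after day 28 + g | 21 | 28 | 49 | 21 |
| At the ETT visit | 21 | 21 | 21 | 0 |
| At the ETT visit | 42 | 28 | 42 | 14 |
| At Safety Follow-up, day 28 | 21 | 28 | 28 | 0 |
| At Safety Follow-up, day 35 | 21 | 28 | 35 | 7 |

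The TE Period includes 28 off-drug days by design. Newly counted events are therefore only those with onset from day 29 to day 28 + g, and only up to P. Protocol 9.1.5.2 asks early discontinuers to keep attending scheduled visits, and 9.1.7 ends their participation at the latest completed visit, up to Week 52. The first two rows are thus what the protocol intends, though not certain for any one subject.

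**Arm-level size (assumed).** The documents do not say how many dates will be incomplete. Take k = 1 to 20 affected subjects in an arm of 200 treated for 52 weeks, with g = 21 to 28.
- Arm exposure: 200 × 364/365.25 = 199.3 patient-years.
- Smallest excess: 1 × 21/365.25 = 0.06 patient-years, or 0.03%.
- Largest excess: 20 × 28/365.25 = 1.53 patient-years, or 0.8%.

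**Effect of a month cap (assumed dates, g = 23, last dose reported only as March).**
- True last dose 20 March, ETT 12 April: the error falls from 23 days to 11 (31 March).
- True last dose 10 March, ETT 2 April: the error falls from 23 days to 21.

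The cap removes the contradiction with the report, but not all of the error.

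**The case against.** The strongest reply is that the rule is discretionary and its effect slight. It ends with an as-appropriate qualifier, so a programmer need not choose a visit date that conflicts with a known month. The primary estimand uses treatment policy (SAP 8.3.1.2), and the key secondary estimands handle intercurrent events in the same way. AE tables show numbers and percentages of subjects (SAP 8.4.1), and no exposure-adjusted AE rate is planned. A later date also errs towards counting events as treatment-emergent, like the rule for missing AE start dates.

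The points on size stand. The qualifier does not rescue the rule: it is undefined, does not confine the result to the reported period, and lets two programmers derive different dates.

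A reader might infer more than the documents support:
- *That the ETT always follows the last dose, so exposure is always overstated.* The ETT is timed from the decision to stop, and a last dose on the same day is not excluded.
- *That the TE Period always lengthens by the full gap.* It is capped at the end of participation. If that is the ETT visit, a gap of up to 28 days adds nothing.
- *That 1% to 2% of all 400 subjects, 4 to 8 people, each gain 21 days.* Completers should have no ETT. Their next source is normally the Week 52 Visit, and Protocol Table 3-2 runs dosing to the evening before it, so the error is about one day. A 21-day error needs an early stop, an incomplete date and a late ETT together. Using the planned 10% drop-out at Week 24 as a rough proxy, 400 × 10% = 40 early stoppers, and the assumed 1% to 2% of these is 0.4 to 0.8 subjects before the late-ETT condition.
- *That EC is the only direct evidence of dosing.* Drug counts are taken at clinic and ETT visits (Table 3-2), and dose times are recorded around PK samples (Protocol 9.6.1).

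**Conclusion.** The point holds as a minor defect in a derivation rule. As written, item 3 can return a last dose date that the reported month or year rules out, against the SAP's practice for medication stop dates and AE end dates. For an affected subject, exposure is too long by up to g days and the TE Period by between 0 and g days, depending on when participation ends. Across an arm, the assumed range gives 0.03% to 0.8% of patient-years. The number affected is not in the documents and is probably very small. No primary or key secondary test is touched. The size rests on assumed gaps and counts; the contradiction with a reported month rests on the text alone.

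**What to change.** Amend Appendix A item 3 before database lock, by the amendment route in SAP Section 3, and separate the two cases.
- **Partial date:** take the earliest of the last day of the reported month (or year, if only the year is known), the ETT or last-visit date, and the end of participation. Do not go below the last complete administration date in EC. If EC shows a dose after the reported period, raise a data query.
- **Fully missing date:** keep a stated value, for example the existing visit-date order, again not before the last complete EC date and not after the end of participation. Calling the visit date merely an upper bound would leave nothing to impute.
- Define the as-appropriate qualifier, or delete it.

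The cost is a few extra programming lines and, for partial dates, a slightly shorter and less inclusive TE window. The change bounds the error and does not remove it.

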Appendix B: Imputation Rules for Missing Prior/Concomitant Medication Dates

Imputation rules for missing or partial medication start/stop dates are defined below:

1. Missing or partial medication start date:
 - a. If only DAY is missing, use the first day of the month.
 - b. If DAY and Month are both missing, use the first day of the year.
 - c. If DAY, Month, and Year are all missing, use a date before the first dose date (in practice, use the informed consent date to impute).
2. Missing or partial medication stop date:
 - a. If only DAY is missing, use the last day of the month.
 - b. If DAY and Month are both missing, use the last day of the year.
 - c. If DAY, Month, and Year are all missing, assign ‘continuing’ status to stop date (in practice, use the End of Study Date to impute).

In summary, the prior, concomitant, or post categorization of a medication is described below.

Table 11-2 Prior, Concomitant, and Post Categorization of a Medication

Medication Start Date	Medication Stop Date			
	< First Dose Date of Run-in TE Period	≥ First Dose Date of Run-in TE Period and < End Date of Run-in TE Period	≥ First Dose Date of Treatment TE Period and ≤ End Date of Treatment TE Period	> End Date of Treatment TE Period
< First Dose Date of Run-in TE Period	P	PC1	PC1C2	PC1C2A
≥ First Dose Date of Run-in TE Period and < End Date of Run-in TE Period	-	C1	C1C2	C1C2A
≥ First Dose Date of Treatment TE Period and ≤ End Date of Treatment TE Period	-	-	C2	C2A
> End Date of Treatment TE Period	-	-	-	A

P: Prior; C1: Concomitant during the Run-in Period; C2: Concomitant during the Treatment Period; A: Post

The same imputation rules will be followed to address missing and/or partial dates for non-pharmacological treatments/procedures.

Appendix C: Details of GLI Equations for Calculating ppFEV₁

Percent predicted values will be calculated for the parameters of FEV₁, FVC, FEV₁/FVC, and FEF_{25%-75%} using the Quanjer GLI-2012 Regression Equations and Lookup Tables.

The regression equations and lookup tables required to implement the Quanjer GLI-2012 predicted values are available in:

Philip H. Quanjer, Sanja Stanojevic, Tim J. Cole, Janet Stocks. Quanjer GLI-2012 Regression Equation and Lookup Tables. Global Lung Function Initiative. [online] Available at: <https://www.ers-education.org/lr/show-details/?idP=138978> [Accessed Sep 2023].

The instructions and tools on how to implement the Quanjer GLI-2012 equations are:

Philip H. Quanjer, Sanja Stanojevic, Tim J. Cole, Janet Stocks. Implementing GLI-2012 regression equations. Global Lung Function Initiative. [online] Available at: <https://www.ers-education.org/lr/show-details/?idP=138979> [Accessed Sep 2023].

Sanja Stanojevic. GLI-2012 - SAS Macro. Global Lung Function Initiative. [online] Available at: <https://www.ers-education.org/lr/show-details/?idP=138988> [Accessed Sep 2023].

The data handling rule for spirometry is as follows:

- Input age with at least 2 decimal places
- Use height at screening, regardless of if height is collected at other study visits, for subjects whose age at informed consent is >21 years. For subjects with age ≤21 years, height collected at the respective visit should be used.
- For race, race is Black if, on the CRF, Black or African American is the only race selected. Race is Northeast Asian if Northeast Asian is the only race selected. Race is Southeast Asian if Southeast Asian is the only race selected. Race is White if White is the only race selected. Race is Other for all other races, including multiple selections.

Appendix D: Estimand Framework for the Primary Efficacy Endpoint

Estimand	Primary Estimand	Alternative Estimand
Treatment	VNZ/TEZ/D-IVA versus ELX/TEZ/IVA	
Population	Study population represented by inclusion and exclusion criteria	
Variable	Absolute change from baseline in ppFEV ₁ through Week 24	
Population-level summary	Difference in variable means between VNZ/TEZ/D-IVA and ELX/TEZ/IVA groups	
Handling of ICE		
Treatment discontinuation	Treatment Policy (i.e., observed ppFEV ₁ values after the ICE will be used, if available)	Hypothetical strategy (i.e., observed ppFEV ₁ values after the ICE will be set to missing)
Use of prohibited medication [†]		
Analysis	Primary Analysis	Supplementary Analysis
Analysis model	MMRM	
Intermittent missing	MMRM	
Treatment discontinuation	MMRM	
Use of prohibited medication	MMRM	
Other reasons	MMRM	

D-IVA: deutivacaftor; ELX: elexacaftor; ICE: intercurrent event; IVA: ivacaftor; MMRM: mixed model for repeated measures; TEZ: tezacaftor; VNZ: vanzacaftor

[†] Prohibited medication includes use of non-study drug CFTR modulators for >3 days in either the Run-in Period or the Treatment Period prior to Week 24

